7.3 Package and Labelling

Both FCM and IS will be supplied to each site already packaged and labelled. All packaging and labelling operations will be performed according to GMP and Good Clinical Practice (GCP) guidelines. Labelling will be in accordance with local study site regulations for investigational products. Ferric carboxymaltose will be packaged in kits containing 1 labelled FCM vial (500 mg per 10 ml). Venofer will be packaged in kits containing 2 ampoules of Venofer (100 mg per 5 ml). Kits will be numbered for tracking purposes. The kit box as well as the vial/ampoule in the kit box will be labelled with the same kit number.

7.4 Study Treatment Allocation

Each eligible subject will be assigned to 1 of the treatment arms using IRT.

7.5 Site Supply, Storage, Accountability

7.5.1 Site Supply

Once a site has been approved to receive study drug, the site will be supplied with an initial stock of study drug. The need for drug resupply will be assessed on a regular basis taking into account the number of subjects enrolled, and the number of subjects in screening, at the site.

7.5.2 Storage

Use of a calibrated thermometer and maintenance of a temperature log is mandatory. The log should be updated by site personnel at least once weekly with the minimum and maximum temperatures for the week being recorded. This log must be available for review by the Monitor during on-site monitoring visits. Should the storage

temperature be outside the range, the medication must be quarantined immediately and the Sponsor must be contacted for guidance.

7.5.3 Accountability

The Investigator at each site is responsible for study drug supplies. The Investigator will ensure that adequate records of the receipt, preparation, administration and return of the study drug are kept and that the study drug is used only for subjects enrolled in the study. All data regarding the study drug must be recorded on the relevant forms provided.

Each study site will maintain a drug inventory/dispensing record for all drugs dispensed and returned. At the end of the study, 1 copy of the drug inventory/dispensing record should be sent to the Sponsor for the central study file. The original will be kept in the site files.

After completion of the study, or if it is prematurely terminated, all materials will be returned to the Sponsor. If the study medication is destroyed at site, the Investigator will forward the certificate of destruction to the Sponsor. The decision to destroy study medication at site must be made by the Sponsor.

7.6 Drug Dose Modification

If extravasation is noted during administration of FCM or IS, dosing should be ceased immediately. Study drug administration may be completed using a different injection site to complete the required dosage. If it is not possible to administer the full dose to a subject, the amount of actual dose administered must be documented on the relevant page of the CRF.

In case of severe anaemia (Hb <6 g/dL), the subject is to be discontinued from the study. Further management of anaemia is at the Investigator's discretion.

7.6.1 Procedures for Overdose

If an inadvertent overdosing of a subject (e.g., by a calculation error of the required iron dose) is detected, this must be reported as an AE (see Section 10, Evaluation, Recording and Reporting of AEs and SAEs).

Post-baseline iron parameters will be assessed at each visit using the central laboratory. In the case of iron accumulation the Investigator at the site will initiate corrective measures according to local guidelines for treatment of iron overload, if necessary.

7.7 Prohibited Therapy and Concomitant Treatment

Prohibited therapies in this study will include the following drugs:

- Oral or other IV iron therapy (other than the study medication). Note: Ongoing use of multivitamins or nutritional supplements containing iron are permitted when doses are lower than 75 mg per day. If the dose of iron in these products is unknown, they should not be administered during the study.
- ESAs
- Blood transfusions

Note: Blood transfusions and ESAs might be used as rescue medication if the subject requires such treatment for symptomatic anaemia therapy. In this case, the subject must be withdrawn from the study and end of study procedures must be completed before transfusion or treatment. The reason for discontinuation and the date must be recorded on the appropriate page of the CRF. The date on which the procedure actually took place must also be recorded in the CRF.

If symptoms of acute iron intoxication occur, treatment will be according to standard medical practice, e.g. consider the use of an iron chelator such as deferoxamine mesylate.

In case of hypersensitivity reactions (including anaphylactoid reactions) or signs of intolerance, an appropriate therapy will be started according to the Investigator's judgement.

Any concomitant treatment given for any reason during the course of the study must be recorded on the CRF and in the subject's medical records, including dosage, start and stop dates and reason for use.

8. RISKS/PRECAUTIONS

8.1 IV irons

Parenterally administered iron preparations can cause hypersensitivity reactions including anaphylactoid reactions, which may be fatal. Therefore, facilities for cardiopulmonary resuscitation must be available. If allergic reactions or signs of intolerance occur during administration, the treatment must be stopped immediately. Hypersensitivity reactions have also been reported after previously uneventful doses of any parenteral iron complexes, including FCM and IS. Each subject should be observed for adverse effects during and for at least 30 minutes following each study drug (FCM or IS) application.

In subjects with liver dysfunction, parenteral iron should only be administered after careful benefit/risk assessment. Parenteral iron administration should be avoided in subjects with hepatic dysfunction where iron overload is a precipitating factor, in particular porphyria cutanea tarda. Careful monitoring of iron status is recommended to avoid iron overload.

Parenteral iron must be used with caution in cases of acute or chronic infection, asthma, eczema or atopic allergies. It is recommended that the administration of FCM or Venofer be stopped in subjects with ongoing bacteraemia. In subjects with chronic infection, a benefit/risk evaluation has to be performed, taking into account the suppression of erythropoiesis (due to chronic infection).

Paravenous leakage must be avoided because leakage of FCM or IS solution at the injection/infusion site may lead to irritation of the skin and potentially long-lasting, brown discolouration at the site of injection/infusion. In the event of paravenous leakage, administration of FCM or IS must be stopped immediately. Study treatment may be re-administered in a different location (i.e. other arm), but extra care needs to be taken to make sure that paravenous leakage does not occur again. This also needs to be clearly documented in the CRF and the source data. If a subject did not receive the full dose, this also needs to be recorded.

8.2 Ferric Carboxymaltose

One mL of undiluted FCM solution contains up to 5.5 mg (0.24 mmol) of sodium. This has to be taken into account in subjects on a sodium-controlled diet.

To date, over 7,300 subjects have received FCM in completed clinical studies. The most commonly reported ADRs that have occurred in 1% to 10% of subjects were headache, dizziness, hypertension, nausea, injection/infusion site reactions, flushing and hypophosphataemia. No reported ADRs were very common ($\geq 10\%$).

Please refer to the latest version of the IB for a full list and description of risks and precautions.

8.3 Iron Sucrose

Subjects administered IS commonly (between 1% and 10%) experience dysgeusia, hypertension, hypotension, nausea, injection/infusion site pain.

Hypotensive episodes following administration of IS have been reported and will be caused if injection/infusion is administered too rapidly. For further details on risks and precautions, please refer to the currently approved Insert Sheet for China.

9. STUDY PROCEDURES

9.1 Description of Study Assessments

9.1.1 Vital Signs

To be performed per Table 1: Schedule of Events. Body temperature, resting blood pressure (systolic and diastolic) and heart rate will be measured with the subject in a sitting position.

9.1.2 Physical Examination

To be performed per Table 1: Schedule of Events.

A full physical examination will be performed at screening and End of Study/ Early Withdrawal visit. Any clinically significant abnormalities occurring before signature of informed consent should be recorded on the medical history page of the CRF and any clinically significant abnormalities occurring or worsening after signature of informed consent should be recorded on the AE page.

9.1.3 Laboratory Parameters

All blood samples (total blood volume approximately 46ml) will be analysed at a central laboratory, Teddy Clinical Research laboratory,
[name]
[name]
[name]
[name]
China.

Blood for clinical chemistry and haematology does not have to be drawn under fasting conditions.

Haematology parameters to be analysed are Hb, haematocrit, red blood cell count, MCV, MCH, MCHC, reticulocyte count, Hb content of reticulocytes, white blood cell count with differential (absolute and percentage) and platelet count.

Iron status parameters include serum iron, serum ferritin, serum transferrin, UIBC and TSAT.

Clinical chemistry parameters to be analysed are electrolyte status (sodium, potassium, magnesium, calcium, chloride, phosphorus), glucose, AST, ALT, GGT, AP, lactate dehydrogenase and hsCRP.

Blood for safety laboratory assessments will be collected at screening, baseline, Weeks 2, 4, 6 and 8. Blood samples must always be collected prior to study drug administration.

A serum pregnancy test (for women of childbearing potential only) will be performed at screening and End of Study visit.

9.1.4 Electrocardiogram

A 12-lead electrocardiogram (ECG) will be performed locally at each participating site at screening, Week 4 and End of Study visit/Early Withdrawal. Heart rate, QT, QTcF, RR interval, QRS complex duration and PR interval values will be assessed. Absolute and change from baseline data will be analysed for interval data, any clinically significant abnormal findings will be recorded in the source documents and as an AE in the CRF. QT and QTc will be analysed in accordance with ICH E14 guidance [16].

The 12-lead ECGs will be recorded and assessed according to local clinical practice. All original ECG traces must be stored in the subject's medical record as source documents. In cases where thermal paper will be used for ECG traces an ECG copy on permanent paper must be produced and also stored in the subject's medical record.

9.1.5 Urinalysis

A urine sample will be collected during the study visits as per Table 1: Schedule of Events, and analysed in the central laboratory to measure urine phosphate, protein, glucose, bilirubin, pH, nitrite, ketone, urobilinogen, blood, leukocytes.

9.2 Schedule of Assessments

For detailed schedule of assessments (including all protocol required assessments, visits and visit windows) please refer to Table 1: Schedule of Events.

9.2.1 Screening and Baseline Procedures

After signing the informed consent and within 7 days prior to the initial treatment administration, relevant demographic (including age, sex and race), key information on IDA (including underlying cause for IDA and date of diagnosis, and previous treatments), and baseline medical history data, including concomitant medications will be collected. Study procedures will be performed per

Table 1: Schedule of Events, to assess subject eligibility for the study.

Consent must be received prior to any procedure completed only for the study and before randomisation or administration of study drug.

Screening laboratory values will be used to assess for subject eligibility (including serum pregnancy tests for females at screening) on relevant blood parameters. Laboratory assessments will be repeated at the baseline visit but not assessed to confirm eligibility criteria.

Eligible subjects will be randomised at the baseline visit to one of the two treatment arm.

Subjects failing to meet eligibility will be considered screen failures and will discontinue study participation. Subjects may be re-screened once. Any subject that is rescreened must have all tests and procedures completed to permit inclusion into the study (i.e., all screening tests and procedures must be completed as per the Schedule of Events with the exception of any inclusion criteria, exclusion criteria and procedures that can use historical results. In case of re-screening, documented informed consent must be obtained again, and the date of informed consent must be a minimum of 4 weeks after the date when the subject was declared a screen failure. The subject will keep their unique subject number.

9.2.2 Treatment Procedures

Subjects randomised to receive FCM will receive the first administration of FCM at baseline (Day 1), and the second and third dose at Day 8 and Day 15, if needed according to the dosing matrix (see Table 2, Section 7.2.1, Arm A: Ferric Carboxymaltose).

Subjects randomised to IS will have their iron deficit calculated according to the Ganzoni formula (see Section 7.2.2, Arm B: Iron Sucrose). The doses will be split into injections of 200 mg iron and administered three times a week until the calculated dose has been given to the subject. The cumulative Venofer dose is to be rounded up or down to the nearest 200 mg. During these dosing visits, no additional data will be collected or procedures performed, except for ongoing information on AEs or change in concomitant medications, including dose. Note: Application of IS and FCM at any visit should be done after all assessments as per Schedule of Event, Table 1, especially blood draw for laboratory assessments, have been performed.

For both treatment groups, time of start and end of administration (including any interruptions) and volume administered (i.e. incomplete dose including reason) must be recorded.

During post-baseline visits at 2, 4 and 6 weeks (± 3 days), the following assessments will be performed:

- Vital signs
- Laboratory assessments (haematology, chemistry, iron parameters, urinalysis)
- AEs and concomitant medications
- ECG (only Week 4)

See

Table 1: Schedule of Events for full details of protocol required procedures and applicable visits (and timings).

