2.1 Design

An efficacy study in Caucasian subjects by Evstatiev et al, 2011 [15] demonstrated that FCM administered using a simplified dosing formula (as proposed in this study) was superior to IS dosed using the Ganzoni formula (at multiple 200 mg iron doses). However, since no data are available on the use of FCM in Chinese patients, a non-inferiority design has been chosen for this study, assuming that FCM treatment is at least as good as IS in Chinese subjects. A randomised design was chosen to reduce bias in baseline differences between the treatment groups.

Due to the differences in posology between the study drug (FCM) and the comparator (IS) additional administrations may be required for subjects receiving IS. In a 65 kg subject with Hb of 9 g/dL at screening, FCM would require 2 individual doses of FCM (1,000 mg iron followed by a single dose of 500 mg iron 1 week later). However, if the same subject was randomised to receive IS, the cumulative dose required (as per label) would be 1,436 mg iron which would require 7 individual 200 mg iron doses (i.e., bi-weekly dosing) starting on Day 1.

Therefore, this study will utilise an open-label design to avoid unnecessary IV placebo injections. This reduces the burden of requiring additional subject visits to both groups (as subjects receiving IS will need more dosing visits than subjects in the FCM group) as well as removing the potential for infection and other side-effects that may result from an IV placebo injection.

IV iron products are designed to deliver, in a controlled way, iron to the body and to replenish iron stores and as a consequence increase Hb concentration. Therefore, the study primary endpoint is the percentage of subjects achieving an increase in Hb \geq 2g/dL (responders) from baseline at any time up to Week 8. Since knowledge of the study drug will not impact this objective parameter, in addition to the fact that all subjects will be receiving IV iron, the open-label design is considered to be the most appropriate design for this study.

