4. INVESTIGATIONAL PLAN

4.1 Overall Study Design

This is an open-label, randomised controlled study to assess the impact of FCM in correcting IDA compared to Venofer (IS) in Chinese subjects. The study will randomise approximately 368 subjects (184 per group) suffering from different underlying diseases leading to IDA. It is expected that approximately 850 subjects need to be screened to randomise 368 subjects.

After an initial screening period (up to 7 days), eligible subjects will undergo baseline assessments and will be randomised (1:1) to receive either FCM or IS at study Day 1.

In the FCM group, study drug administration will occur on Day 1 and, if needed, on Day 8 and Day 15. Subjects randomised to IS will receive injections/infusions of a maximum of 200 mg iron three times a week until the calculated total iron dose is administered.

All subjects will return for assessment of efficacy and safety at Weeks 2, 4, 6 and 8. The schedule of assessments is provided in Table 1: Schedule of Events.

Randomised subjects who terminate their study participation for any reason regardless of whether the study drug was taken or not, will retain their randomisation number. The next subject will be given the next randomisation number.

The Investigator is responsible for ensuring that consideration is given to the post study care of the subject's medical condition.

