7.2.2 Arm B: Iron Sucrose

For subjects in the individually calculated IS dosage regimen group, the individual iron deficit will be calculated using the formula of Ganzoni [9]:

Cumulative iron deficit [mg] =

$$BW [kg] \times (\text{target Hb}^{(1)} - \text{actual Hb}) [g/dL]^{(2)} \times 2.4^{(3)} + 500 \text{ mg}^{(4)}$$

⁽¹⁾ Target Hb for BW >35 kg = 15 g/dL, respectively 9.3 mmol/L

⁽²⁾ To convert mmol/L to g/dL: multiply Hb (mmol/L) by the factor 1.61145

⁽³⁾ Factor 2.4 = 0.0034 (iron content Hb = 0.34%) x 0.07 (blood volume = 7% of BW) x 10,000 (conversion g/dL to mg/L)

⁽⁴⁾ Iron storage depot

Note: BW = Body weight.

The calculated cumulative IS dose is to be rounded up or down to the nearest 200 mg.

Subjects will receive single doses of IS of up to a maximum single dose of 200mg iron three times a week. Depending on the calculated iron deficit, up to 11 IS injections will be given.

Iron Sucrose (Venofer) will be administered by slow IV push injection at a rate of 1 ml undiluted solution per minute (10 ml of the product in at least 10 minutes; administration time should not exceed 60 minutes) or by drip infusion in a dilution of 1 ml of Venofer in maximum 20 ml 0.9% w/v physiological saline (10 ml of the product in maximum 200 ml saline). Venofer must be used immediately after dilution. The drip infusion rate should be 200 ml solution in at least 30 minutes, and should not exceed 60 minutes.

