Adverse events persisting at the time of study completion will be followed by the Investigator through contact with the subject until resolution or stabilisation or the subject is lost to follow-up and cannot be contacted. The outcome must be documented in the subject's source documents.

If the subject reports an AE, it is the Investigator's responsibility to acquire sufficient information in order to assess causality. This may require additional laboratory testing, physical examinations, telephone contacts, etc.

In order to avoid bias in eliciting AEs, subjects should be asked a non-leading question, such as "How are you feeling?" It is also important to question the subject in a non-leading way about changes in their health or concomitant medication usage since their last visit. This information should be collected prior to completion of assessments at all study visits. In addition, any symptoms/conditions reported during assessments and deemed to be clinically significant by the Investigator will be assessed as AEs.

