- The date of the first (last) day of the month, if month and year are available but day is missing.
- The date of the first (last) day of the year, if year is available but day and month are missing.
- A very early (late) date, e.g., 01JAN2000 (01JAN2100), if the date is completely missing.

The imputation method will only be used to determine treatment emergence and to determine the time of the event relative to the first administration of study medication. A worst-case approach will be followed in the event of missing severity or causality data. If the severity is missing, 'Severe' will be imputed. If causality data is missing, 'Certain' will be imputed. In the event that no coding information is available for a specific AE, the AE will be presented as an 'Uncoded' in summary tables.

The following listings will also be generated:

- Treatment Emergent Adverse Events Listing
- Non-Treatment Emergent Adverse Events
- Adverse Events (Screened Only/Not Treated)
- Treatment Emergent Treatment Related Adverse Events
- Treatment Emergent Serious Adverse Events
- Treatment Emergent Adverse Events Leading to Premature Study Withdrawal
- Treatment Emergent Adverse Event Leading to Death
- Special Situations

The following summary tables will be provided:

- Overall Summary of Treatment Emergent Adverse Events
- Treatment Emergent Adverse Events by Primary System Organ Class and Preferred Term
- Treatment Emergent Treatment Related Adverse Events by Primary System Organ Class and Preferred Term
- Treatment Emergent Serious Adverse Events by Primary System Organ Class and Preferred Term
- Treatment Emergent Treatment Related Serious Adverse Events by Primary System Organ Class and Preferred Term
- Treatment Emergent Adverse Events Leading to Premature Study Withdrawal by Primary System Organ Class and Preferred Term
- Treatment Emergent Adverse Events Leading to Death by Primary System Organ Class and Preferred Term
- Treatment Emergent Adverse Events Leading to Study Drug Interruption by Primary System Organ Class and Preferred Term
- Treatment Emergent Adverse Events by System Organ Class, Preferred Term, and Relationship to Study Medication
- Treatment Emergent Adverse Events by System Organ Class, Preferred Term, and Maximum Severity
- Treatment Emergent Adverse Events by Preferred Term

Each summary table will include incidences of adverse events.

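### More frequent adverse-event contact on iron sucrose during dosing may raise its crude TEAE incidence, and no planned table compares the arms on equal ascertainment

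*Protocol*

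**What the plan says.** Comparative safety of FCM and IS is a stated secondary objective (Protocol 3.2).

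IS is "administered three times a week until the calculated dose has been given to the subject" (Protocol 9.2.2), and Protocol 7.2.2 foresees that "up to 11 IS injections will be given". At these visits "no additional data will be collected or procedures performed, except for ongoing information on AEs or change in concomitant medications, including dose" (Protocol 9.2.2). For the other arm, Protocol 4.1 says: "In the FCM group, study drug administration will occur on Day 1 and, if needed, on Day 8 and Day 15". Both arms attend at Weeks 2, 4, 6 and 8.

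On elicitation, Protocol 10.3.1 says that "subjects should be asked a non-leading question", and the enquiry covers the time since the previous visit. Recurrences of a resolved AE are recorded separately.

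SAP 4.7.1 reports AEs per subject and per event, by treatment group over the whole study: "Each summary table will include incidences of adverse events". It plans breakdowns by severity, relationship, seriousness and events leading to withdrawal. Neither document mentions the difference in contact frequency or plans a table that equalises it, and SAP 4.9 plans no other analyses.

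**The concern.** How often subjects are asked affects how many minor events are recorded. During IS dosing the look-back is two or three days; on FCM it is one to two weeks. A brief headache or flush is more likely to be recorded under the shorter look-back. Per-event counts are the most sensitive, because each recurrence is a new record.

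The direction is predictable and favours the sponsor's product. It also matches what the rationale sections expect (Protocol 2, SAP 1.1): that fewer administrations carry fewer administration-related risks. A lower crude TEAE incidence on FCM would look like confirmation, yet the planned tables cannot separate a real effect of fewer injections from less frequent asking. The open-label justification in Protocol 2.1 rests on Hb being objective, which does not extend to subject-reported AEs. Protocol 10.3.1 controls how the question is worded, not how often it is put.

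**Working it through.** **Inputs.** Ganzoni formula, target Hb 15 g/dL, factor 2.4, 500 mg stores and rounding to 200 mg: Protocol 7.2.2. FCM doses: Protocol 7.2.1, Table 2. Common visits and ±3 day windows: Protocol Table 1.

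**Assumptions.** IS is given on Days 1, 3, 5, 8, 10, 12, 15 and so on, since the documents do not fix the weekdays. A dosing visit inside a window counts as the same contact as the scheduled visit. The FCM Day 8 dosing visit counts as an AE contact; this is conservative, because the AE sentence in Protocol 9.2.2 sits in the IS paragraph.

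**1. Reproduce the plan's example (65 kg, Hb 9 g/dL).** 65 × (15 − 9) × 2.4 + 500 = 1,436 mg, and 1,436 / 200 = 7.18, so 7 doses. Protocol 2.1 agrees: "the cumulative dose required (as per label) would be 1,436 mg iron", "which would require 7 individual 200 mg iron doses". The same subject receives two FCM doses, on Day 1 and Day 8.

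**2. Count AE contacts after Day 1.**
- IS to Week 4: Days 3, 5, 8, 10, 12 and 15 (Day 15 doubling as Week 2), plus Week 4 = 7.
- FCM to Week 4: Day 8, Week 2, Week 4 = 3. Ratio 7/3 = 2.3.
- To Week 8, adding Weeks 6 and 8 in both arms: 9 against 5, ratio 1.8. Counting Day 1 as well: 10 against 6, ratio 1.7.
- Common visits only: 4 against 4, ratio 1.0.

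If Week 2 is held separately from an IS dosing visit, the Week 4 count is 8 against 3 (2.7). If AEs are not asked about at the FCM Day 8 visit, it is 7 against 2 (3.5). Protocol 2.1 describes the seven-dose course as bi-weekly, while 7.2.2 and 9.2.2 say three times a week; these passages must be reconciled. At two doses a week the count to Week 4 is still 7 against 3.

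**3. Other subjects, to Week 4.**

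| Subject | Ganzoni (mg) | IS doses | IS contacts | FCM contacts | Ratio |
|---|---|---|---|---|---|
| 45 kg, Hb 8 | 45 × 7 × 2.4 + 500 = 1,256 | 6 | 6 | 3 | 2.0 |
| 60 kg, Hb 10.5 | 60 × 4.5 × 2.4 + 500 = 1,148 | 6 | 6 (7 if Week 2 is separate) | 2 | 3.0 (3.5) |
| 80 kg, Hb 7 | 80 × 8 × 2.4 + 500 = 2,036 | 10 | 10 | 3 | 3.3 |

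Over an assumed, unweighted grid (40–85 kg, Hb 6.0–10.9 g/dL) the median ratio is 2.67, with 5th to 95th percentile 2.0 to 3.3. This is not a forecast for the enrolled population.

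**4. Where the excess lies.** In the 65 kg example IS dosing ends on Day 15, and the schedules then coincide. The whole excess falls in Days 1–15, when the FCM subject is asked on Day 8 and at Week 2: a look-back of about 7 days, against 2–3 on IS. A two-week look-back during IS dosing arises only for a one-dose FCM subject.

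**5. Sensitivity, not an estimate.** Assume equal true rates, Poisson events and 50% recorded TEAE incidence on FCM (about the figure in Protocol 1.2.4). Let s be the share of events arising in the first 4 weeks and c the relative gain in IS capture there. Recorded IS incidence is 1 − exp(−ln 2 × (1 + s × c)). For s from 0.5 to 0.8:
- c = 10%: 51.7% to 52.7%
- c = 20%: 53.3% to 55.2%
- c = 50%: 58.0% to 62.1%

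Neither s nor c is in the documents. Where unequal contact stops at Day 15, a smaller share of events is exposed to it.

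**The case against.** Unequal contact follows from the regimens, and placebo injections were avoided deliberately to spare subjects burden and risk (Protocol 2.1, 6.2). There are partial safeguards: the question covers the whole interval since the last visit, spontaneous reports and unscheduled visits are captured, and both arms are observed for at least 30 minutes after each dose. Laboratory, vital-sign and ECG findings come from common visits. The severity table lets a reader discount mild events. No between-arm AE test is planned, so no error rate is at stake.

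Most of this stands, and it limits the point to mild, transient, subject-reported events and to interpretation. It does not remove it. The recall question recovers only what is remembered, and the severity table shows how many mild events each arm recorded but not whether they were sought equally.

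A reader might infer more than the documents support:
- That contact is two to three times as frequent throughout. That range applies to the first 4 weeks; the tables cover the whole study, where the example gives 1.8.
- That IS will certainly show an excess of known size. Any figure depends on assumed capture rates.
- That a lower FCM rate would be pure artefact. More injections may cause more real events.

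**Conclusion.** The concern holds as a limit on interpreting a descriptive secondary comparison. IS subjects have more AE contacts during dosing: 7 against 3 to Week 4 and 9 against 5 to Week 8 in the protocol's example, given the visit placement assumed above. At equal true rates the crude TEAE tables may therefore record more mild, short-lived events on IS, which favours FCM. Direction and contact ratio follow from the documents; the size of any distortion does not. SAEs and scheduled laboratory, vital-sign and ECG findings are little affected, and the primary endpoint is untouched. The plan does not support reading a difference in crude overall TEAE incidence, by itself, as better tolerability, and it offers no like-for-like table in its place.

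**What to change.** Add to SAP 4.7.1 and Appendix 3, by arm, from dates and times already collected:

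1. TEAEs ongoing on the common Week 2, 4, 6 and 8 visit dates.
2. TEAEs with onset during or within 30 minutes after an administration, per subject and per administration. Both arms are directly observed for that period (Protocol 7.2.3, 8.1). Administration times are recorded, as is AE onset time on dosing days. A 24-hour window would not work: onset time is collected only for AEs starting on dosing days (Protocol 10.3.1), and next-day events would still be elicited unequally. State how an AE on a dosing day with no onset time is handled, because the SAP 4.7.1 imputation places events only relative to the first administration.
3. Optionally, TEAEs with onset from Day 29, labelled as a post-dosing period that does not measure tolerability of administration.

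State in the SAP that AE contact frequency differs between arms during dosing, so a difference in crude overall TEAE incidence is not by itself evidence of better tolerability.

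The cost is two or three extra tables, with no new visits or data. Table 1 omits events that resolve between visits; the existing tables still show them.
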